#### **5.1.2.6. Increases in Urinary Protein**

Increases in urinary albumin have been observed in some patients treated with bardoxolone methyl with chronic kidney disease. The increases are likely due to bardoxolone methyl's pharmacological modulation of tubular protein reabsorption and have not been associated with interstitial fibrosis or injury. In preclinical studies, bardoxolone methyl has been shown to downregulate the primary proteins involved in protein reabsorption in the proximal tubules: the megalin-cubilin complex ([Reisman, 2012](#)). Moreover, the magnitude of observed eGFR increases with bardoxolone methyl treatment is thought to reduce the residence time of protein in the proximal tubules, thereby reducing protein reuptake and increasing urinary protein levels.

Therefore, increased eGFR, together with decreased megalin expression, is thought to result in decreased fractional absorption of albumin and increased urinary excretion of albumin.

Consistent with bardoxolone methyl-mediated protection in preclinical models of protein-overload-induced nephropathy, these pharmacological effects are thought to reduce protein overload and secondary nephropathy caused by excessive albumin uptake and therefore are not associated with tissue injury and interstitial fibrosis ([Rossing, 2019](#)).

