### 7.6.1. Screening Period (Screen A & Screen B Visits)

No screening procedures may be completed prior to obtaining written informed consent. The Screening Period includes 2 visits (Screen A and Screen B), and the duration of screening (from Screen A to Day 1) may not exceed 4 weeks. The Screen A and B visits may be completed on consecutive days.

The Screen A visit must include the following assessments:

- Obtain informed consent prior to any screening procedures being performed
- Obtain demographics information (date of birth, sex, ethnicity, race)
- Record medical history, including CKD etiology and historical serum creatinine
- Perform vital sign assessments (sitting blood pressure as outlined in Section 9.10.10, pulse, heart rate, temperature, height, and weight)
- Review and record concomitant medications
- Perform 12 lead ECG (at rest)
- Perform a full physical examination
- Collect blood and urine specimens for clinical laboratory tests:
  - Serum pregnancy test (for WOCBP)
  - Clinical chemistry, including eGFR
  - BNP and NT-proBNP
  - Hemoglobin A1c
  - Hematology
  - Urinalysis and microscopy
- Assess patient eligibility
- Dispense specimen collection cup and provide instructions for collection of first morning void

The primary purpose of the Screen B visit is to obtain the 2nd baseline eGFR value.

The Screen B visit must include the following assessments:

- Review and record concomitant medications
- Perform urine pregnancy test, if applicable
- Collect blood for clinical chemistry, including eGFR
- Collect urine for UACR (first morning void brought to clinic by patient)

Blood pressure may be taken on Screen B for Inclusion criteria eligibility.

Once all screening data have been collected, eligibility for the patient should be considered, and only after confirmation the patient meets all eligibility criteria should the patient be assigned a treatment kit in the RTSM system or return for Day 1 procedures.

Patients may repeat screening once to qualify for the study (re-screening must occur at least 2 weeks after the screen fail). If a patient is approved to re-screen, they are given a new patient number and all screening procedures are completed.

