### **9.1.6. Management of Urinary Protein**

Although increases in urinary protein with bardoxolone methyl have not been associated with kidney injury or loss of kidney function, investigators should closely monitor patients if urinary albumin to creatinine ratios increase by more than 100% and exceed 1000 mg/g for proteinuria and should consult the medical monitor for appropriate measures.

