**Diagnosis and main criteria for inclusion**

## Inclusion criteria:

1. Male and female patients  $18 \leq \text{age} \leq 75$  upon study consent;
2. Diagnosis of CKD with screening eGFR (average of Screen A and Screen B eGFR values)  $\geq 20$  to  $< 60 \text{ mL/min/1.73 m}^2$ 
  - a. The two eGFR values collected at Screen A and Screen B visits used to determine eligibility must have a percent difference  $\leq 25\%$ ;
3. Patient must meet at least one of the following criteria:
  - a. UACR  $\geq 300 \text{ mg/g}$ ; OR
  - b. eGFR decline at a rate of  $\geq 4 \text{ mL/min/1.73 m}^2$  in prior year; OR
  - c. Hematuria (glomerular) defined as  $> 5\text{-}10$  red blood cells (RBCs) per high power field (HPF, manual method), or documented history of positive urinary dipstick for blood in prior year, or macroscopic hematuria in prior 3 years;
4. Systolic blood pressure  $\leq 150 \text{ mmHg}$  and diastolic blood pressure  $\leq 90 \text{ mmHg}$  at Screen A or Screen B visit after a period of rest ( $\geq 5$  minutes);
5. Treatment with an angiotensin-converting enzyme inhibitor (ACEi) and/or an angiotensin II receptor blocker (ARB) at the maximally tolerated labeled daily dose for at least 6 weeks prior to the Screen A visit and with no anticipated changes to dose(s) during study participation. If treatment with ACEi and/or ARB is contraindicated or not indicated, the patient must not have been exposed to an ACEi and/or ARB for at least 8 weeks prior to the Screen A visit;
6. Absolute neutrophil count  $> 1.5 \times 10^9/\text{L}$ , platelets  $> 100 \times 10^9/\text{L}$ , hemoglobin (Hgb)  $\geq 8.0 \text{ g/dL}$ ;
7. Total bilirubin (TBL), alanine aminotransferase (ALT), and aspartate aminotransferase (AST)  $\leq 1.5\text{X}$  the upper limit of normal (ULN) both at Screen A and Screen B visits;
8. Able to swallow capsules;
9. Willing and able to comply with scheduled visits, treatment plan, laboratory tests, and other study procedures;
10. Evidence of a personally signed and dated informed consent document indicating the patient has been informed of all pertinent aspects and risk of the study prior to initiation of any protocol-mandated procedures.

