### **5.4.4. Urine Albumin to Creatinine Ratio**

Baseline UACR is defined as the last value - collected prior to the study drug administration.

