#### **5.5.6.1. Baseline Urine Albumin to Creatinine Ratio (UACR) Categorical Status**

Baseline UACR status will be grouped by the following categories using baseline UACR (see Section 5.4):

- UACR <=300 mg/g
- UACR > 300 mg/g

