#### 9.5.2. Categorical Summaries of Laboratory Results

Select laboratory parameters will be summarized using shift tables. Shift tables are summarized by treatment, laboratory category (hematology, chemistry, urinalysis, and microscopy), and laboratory test and present shifts from baseline status (Normal, Low, High) to worst on study treatment status (Normal, Low, High). The worst abnormality values are defined as the maximum values while on study treatment, with the exception of magnesium and hemoglobin. The worst abnormal values for magnesium and hemoglobin are defined as the minimum values while on study treatment.

Additionally, laboratory parameters of specific interest (ALT, AST, UACR) are summarized using shift tables that summarize shifts from (1) baseline status to end of treatment status, (2) worst on-treatment status to worst off-treatment status (3) worst on-treatment status to Day 35 off-treatment status, and (4) baseline status to worst on-treatment status (5) baseline to worst off-treatment, and (6) worst on-treatment status to best (lowest) off-treatment status. The number and percentage of patients are summarized. For UACR, summaries will present shifts from/to the categories listed in Section 5.5.6.1. For ALT and AST, summaries will present shifts from/to the following categories:

- $\leq$  ULN
- $>$  ULN to  $\leq$  3x ULN
- $>$  3x ULN

In addition, a summary table is provided for the number and percentage of patients meeting the following threshold levels at any time during the study:

- $>$  5x ULN for more than 2 weeks
- $>$  3x ULN and (TBL  $>$  2x ULN or INR  $>$  1.5)
- $>$  3x ULN with the appearance of fatigue, nausea, vomiting, right upper quadrant pain or tenderness, fever, rash, and/or eosinophilia ( $>$  5%).

- BNP > 200 pg/mL
- Magnesium < 1.3 mEq/L (0.65 mmol/L)
- NT-proBNP > 1000 pg/mL

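### The UACR shift tables have one cut at 300 mg/g, so patients who start above it cannot shift upward from baseline, and no laboratory table counts patients with large rises

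*SAP*

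**What the plan says.** SAP 9.5.2 plans six shift tables for ALT, AST and UACR. Tables 1, 4 and 5 start from baseline and run to end of treatment, worst on-treatment and worst off-treatment status. Tables 2, 3 and 6 start from worst on-treatment status. For the categories it says: "For UACR, summaries will present shifts from/to the categories listed in Section 5.5.6.1".

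Section 5.5.6.1 was written to classify patients at entry: "Baseline UACR status will be grouped by the following categories using baseline UACR". Its categories are <=300 mg/g and >300 mg/g. On the baseline value, SAP 5.4.4 says: "Baseline UACR is defined as the last value - collected prior to the study drug administration". The only scheduled pre-dose UACR sample is at Screen B (Protocol 7.6.1; the Day 1 list in 7.6.2 has none).

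Inclusion criterion 3a is UACR of 300 mg/g or more. It is one of three routes in: "Patient must meet at least one of the following criteria". Baseline UACR above 300 mg/g also sets the higher maximum dose (SAP 3.1).

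On the drug effect, Protocol 5.1.2.6 reports: "Increases in urinary albumin have been observed in some patients treated with bardoxolone methyl with chronic kidney disease". Protocol 9.1.6 gives a monitoring criterion: "investigators should closely monitor patients if urinary albumin to creatinine ratios increase by more than 100% and exceed 1000 mg/g for proteinuria". The threshold summary at the end of SAP 9.5.2 covers transaminases, BNP, magnesium and NT-proBNP, and has no UACR item.

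Elsewhere, SAP 9.5.1 plans geometric-mean UACR ratios to baseline with 95% confidence intervals, MMRM and ANCOVA on the ratio, a summary by baseline UACR quartile, and box plots that name UACR.

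**The concern.** A shift table is meant to show how many patients moved to a worse state. Here the cut nearly coincides with an entry criterion, and nothing lies above it. Patients with the most albuminuria at entry, who are also those assigned the higher maximum dose, are already in the worst state the table recognises.

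The worsening cells for that group will be zero in both arms by construction. A reader of the safety report could take the zeros as reassurance about a change that the protocol itself reports in some treated patients and asks investigators to watch.

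UACR also fares worse than its neighbours in the same section. ALT and AST have three categories, and entry at no more than 1.5 times the upper limit of normal leaves room to move up. The 9.5.2 threshold list takes over three of the four transaminase criteria in Protocol 9.1.2 and the magnesium threshold in 9.1.5. The UACR criterion in 9.1.6 has no counterpart.

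**Working it through.** The plan states no figure for these tables, so there is none to reproduce. The main result follows from the definitions.

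**1. The category rule.** From SAP 5.5.6.1, let C(u) = 0 if u <= 300 mg/g and C(u) = 1 if u > 300 mg/g. An upward shift from baseline b to a later value u needs C(u) > C(b).

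- If b > 300, then C(b) = 1, the maximum. The number of upward shifts is 0 for every u.
- If b <= 300, an upward shift needs u/b > 300/b.

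The last two columns below apply the 9.1.6 criterion (rise above 100% and value above 1000 mg/g) and a top category split at 1000 mg/g.

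| Baseline (mg/g) | Ratio | Later value (mg/g) | Upward shift as planned | Meets 9.1.6 criterion | Upward shift if split at 1000 |
|---|---|---|---|---|---|
| 20 | 4 | 80 | no | no | no |
| 299 | 1.5 | 448.5 | yes | no | yes |
| 299 | 4 | 1,196 | yes | yes | yes |
| 301 | 4 | 1,204 | no | yes | yes |
| 600 | 2.1 | 1,260 | no | yes | yes |
| 1,500 | 2.1 | 3,150 | no | yes | no |

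**2. Who is affected.** The Screen B sample normally serves both eligibility and baseline. A patient qualifying on 3a therefore starts in the top category unless the value is exactly 300, because entry is >=300 and the category is >300. All patients assigned the higher maximum dose have baseline above 300 by definition. Patients entering on eGFR decline or hematuria with UACR of 300 or less can still shift upward.

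**3. Which tables.** The zero is exact for tables 1, 4 and 5. In table 2, a patient whose on-treatment values had all fallen to 300 or less could move up off treatment, but that is not on-treatment worsening.

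**4. Illustration of size (assumed inputs, none from the documents).** Take ln(baseline) as normal with SD 1.5, centred so that 30%, 50% or 70% of patients exceed 300 mg/g. Take ln(ratio) as normal with mean ln(GMR), for a geometric mean ratio (GMR) of 1.0, 1.5 or 2.0, and SD 0.6. Simulation with 400,000 patients per setting gives:

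- Patients with baseline above 300 who meet the 9.1.6 criterion: 10% to 47%. Those who can show an upward shift: 0%.
- Of all patients meeting the criterion, 1% to 11% appear as an upward shift in the planned table.
- Of all patients whose UACR more than doubles, 18% to 30% appear as an upward shift.

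The 10% end is the no-effect setting (GMR 1.0), so some patients meet the criterion by variation alone.

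**5. Chance crossing of 300 (assumed within-patient SD of ln UACR, s = 0.3 to 0.5).** For a stable patient with true value m and three independent on-treatment samples (Weeks 4, 8 and 12):

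P(worst > 300) = 1 - [Phi(ln(300/m)/s)]^3

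- m = 250: ln(300/250) = 0.182. A single sample exceeds 300 with probability 0.27 to 0.36, and the worst of three with probability 61% to 74%.
- m = 150: 3% to 23%.
- m = 100: 0% to 4%.

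**The case against.** The strongest reply is that UACR is already well analysed. SAP 9.5.1 models the ratio to baseline, and the quartile summary shows high-baseline patients separately. Box plots show between-patient spread as well as averages, and patient listings hold every value. A clinically significant laboratory change is also recorded as an adverse event and counted there. All of this stands. A reader might infer from the shift tables that worsening above 300 mg/g would go unseen; the documents do not support that. The gap is a patient count on a fixed criterion. Geometric means, quartile summaries and box plots do not give one, and adverse-event counts depend on each investigator's judgement.

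A second reply is that 300 mg/g is not arbitrary. It is the dose-defining cut and the upper albuminuria boundary in SAP Table 6. That justifies it for subgroups. It does not make it suitable as the only boundary in a table of worsening. Moving to Table 6's three classes would not help, because its top class is also >300 mg/g.

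A third reply is that chance crossing of the line is no reason to change the tables. This is fair. A reader might infer from the 61% to 74% figure that the tables mainly register noise. That figure belongs to one chosen patient at 250 mg/g under an assumed SD, it falls quickly at lower values, and placebo patients face the same risk. Without a baseline distribution, which the documents do not give, the inference fails. New cuts also carry chance crossings: by the same formula a stable patient at 850 mg/g has a 65% to 75% chance that the worst of three values exceeds 1000.

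**Conclusion.** The point holds for the baseline-anchored shift tables. For every patient with baseline UACR above 300 mg/g, the upward-shift count is zero whatever the rise. This rests on the definitions alone and needs no assumed figure. How many patients it covers is unknown, because the documents do not give the share above 300 mg/g. The 10% to 47% range is an illustration under assumed distributions and should not be quoted as an expected result.

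Two further readings go too far. A reader might infer that the tables hide a worsening the drug is known to cause. Protocol 5.1.2.6 says only that increases were seen in some treated patients, and the protocol states that they have not been associated with kidney injury. A reader might also infer that the trial population as a whole starts at the ceiling. Criterion 3a is one of three alternatives, so that does not follow.

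The consequence is confined to descriptive safety reporting. SAP 9 plans no formal safety testing, and the primary eGFR analysis is untouched. It is a modest gap that is cheap to close.

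**What to change.** 1. In the UACR shift tables of SAP 9.5.2, replace the reference to the 5.5.6.1 categories with <=300, >300 to <=1000 and >1000 mg/g.
2. Add to the 9.5.2 threshold summary the number and percentage of patients, by arm and by baseline UACR (<=300 and >300 mg/g), whose UACR rises by more than 100% from baseline and exceeds 1000 mg/g. This uses the protocol's own 9.1.6 criterion for tabulation only and changes nothing in patient management.
3. Keep the two-category grouping of 5.5.6.1 for dose and subgroup use.

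The split alone leaves a ceiling above 1000 mg/g. The count in item 2 does not have one: 1,500 to 3,150 mg/g is counted. A further cut at 30 mg/g, or a count on doubling alone, is not needed to close this gap.

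The cost is SAP wording and table programming, with no new data. Each shift table grows from 4 to 9 cells per arm (2 x 2 to 3 x 3) with about 35 patients per arm, so cells will be small. Some patients in both arms will cross by chance, so the counts should be read against placebo.

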## 8.2. Subject Exclusion Criteria

All patients with any of the following conditions or characteristics must be excluded from the study:

1. Prior exposure to bardoxolone methyl;
2. CKD secondary to or associated with any of the following:
  - a. History of rapidly progressive glomerulonephritis (RPGN)
  - b. Glomerulonephritis requiring immunosuppression in the 6 months prior to Screen A
3. Concomitant use of tolvaptan. Patients previously treated with tolvaptan must have discontinued drug for at least 3 months prior to Screen A visit;
4. Patients treated with polycystic kidney disease-modifying agents (somatostatin analogues) within 3 months prior to the Screen A visit;
5. Systemic immunosuppression for more than 2 weeks, cumulatively, within the 12 weeks prior to Day 1 or anticipated need for immunosuppression during the study;
6. Patients currently taking a sodium/glucose cotransporter-2 inhibitor (SGLT2i), requiring dose adjustments within 12 weeks prior to Day 1 or if dose is anticipated to change during study participation;
7. B-type natriuretic peptide (BNP) level > 200 pg/mL at Screen A visit;
8. Uncontrolled diabetes (HbA1c > 11.0%) at Screen A visit;
9. Serum albumin < 3 g/dL at Screen A visit;
10. Kidney or any other solid organ transplant recipient or a planned transplant during the study;
11. Acute dialysis or acute kidney injury within 12 weeks prior to Screen A visit or during Screening;
12. History of clinically significant cardiac disease, including but not limited to any of the following:
  - a. Clinically significant congenital or acquired valvular disease
  - b. Left ventricular ejection fraction < 40% (based on historical echocardiogram)
  - c. History of hospitalization for heart failure within 12 months prior to Screen A
  - d. New York Heart Association Class III or IV congestive heart failure (CHF)
  - e. Symptomatic coronary disease (prior myocardial infarction, percutaneous coronary intervention, coronary artery bypass graft surgery, or unstable angina) within 12 months prior to Screen A
  - f. Pericardial constriction (based on historical echocardiogram)
  - g. Restrictive or congestive cardiomyopathy (based on historical echocardiogram)
  - h. Uncontrolled atrial fibrillation

- i. History of unstable arrhythmias;
13. Systolic blood pressure < 90 mm Hg at Screen A visit after a period of rest;
14. Body mass index < 18.5 kg/m^2 at the Screen A visit;

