#### 9.1.1. Management of Fluid Status

Specific risk mitigations procedures will be employed to reduce the potential for bardoxolone methyl-induced fluid overload. These procedures include exclusion of patients with any severe kidney disease, defined as an eGFR value of  $< 20 \text{ mL/min/1.73 m}^2$ . To exclude patients with significant cardiac dysfunction, the study will exclude patients with a history of clinically significant cardiac disease. Patients who have evidence of volume overload at baseline, defined as BNP level of  $> 200 \text{ pg/mL}$ , will also be excluded.

Laboratory data and rapid weight gain will also be used to monitor fluid status after randomization. Patients who experience a BNP  $> 100 \text{ pg/mL}$  that represents a doubling (or more) of BNP levels from Day 1 should have an unscheduled telephone contact immediately (see Section 9.10.15 for description of telephone contact). In addition, patients will be given a Sponsor-provided scale to use at home to collect and record their weights daily during the first 8 weeks of the treatment period and weekly thereafter. Patients who experience a five-pound (2.3 kilograms) or greater increase in weight since their Day 1 weight during the first 8 weeks must have an unscheduled telephone contact immediately. Whether due to BNP elevations or weight gain, if clinically important fluid retention is suspected, the patient must be instructed to stop taking their study medication immediately and be medically evaluated by the investigator or a local physician within 1 to 2 days.

Investigators are encouraged to consider starting or increasing doses of diuretics (thiazides, loop diuretics) early after recognition of edema. This can be done concurrently with temporary drug discontinuation and re-initiation. Patients may not restart their study medication until the investigator has completed and documented an assessment of fluid overload.

Beyond Week 8, patients who experience a weight increase of five pounds (2.3 kilograms) or greater compared to Day 1 will be instructed to contact the clinic to assess the need for an unscheduled physical examination and laboratory assessment by the investigator. Study medication should not be discontinued unless clinically important fluid retention is suspected. If suspected, the patient must be instructed to stop taking their study medication immediately and be medically evaluated by the investigator or a local physician within 1 to 2 days.

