#### 9.1.2. Management of Elevated Aminotransferase Levels (ALT and/or AST)

Nearly all instances of elevated aminotransferases due to bardoxolone methyl treatment are expected to be asymptomatic. Some patients may experience more rapid increases in ALT/AST

values than others during the dose titration period. Investigators may consider extending the time between each dose increase from two weeks to four weeks to manage ALT/AST elevations.

Check aminotransferase levels (as well as TBL, GGT, alkaline phosphatase (ALP), and International Normalized Ratio [INR]) within 72 hours if the following occurs:

- ALT or AST levels  $> 3X$  ULN.

Repeat testing every 72 to 96 hours until aminotransferase levels are below  $3X$  the ULN for at least one week. Patient should be followed until aminotransferase level returns to normal. Testing for patients not located near the investigator (such that it is impractical to return to the site at the required intervals) may be performed at a local lab and sent to the investigator and medical monitor for review, by approval from the medical monitor.

Discontinue study drug administration permanently if any of the following occur:

- ALT or AST  $> 8X$  ULN;
- ALT or AST  $> 5X$  ULN for more than 2 weeks;
- ALT or AST  $> 3X$  ULN and (TBL  $> 2X$  ULN **or** INR  $> 1.5$ );
- ALT or AST  $> 3X$  ULN with the appearance of fatigue, nausea, vomiting, right upper quadrant pain or tenderness, fever, rash, and/or eosinophilia ( $> 5\%$ ).

The hepatobiliary tree must be visualized (e.g., ultrasound, magnetic resonance imaging [MRI]) and assessed if a patient discontinues taking study drug secondary to elevated transaminase levels. Additional tests and imaging may be warranted depending on the clinical presentation.

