### 9.5.2.1. Transaminase

Evaluation of Drug-Induced Serious Hepatotoxicity (eDISH) plots are generated for ALT and AST versus TBL.

A listing of subjects with abnormal ALT, AST, or TBL will also be provided.

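### The SAP's laboratory threshold table counts three of the protocol's four ALT/AST permanent-discontinuation criteria and leaves out ALT or AST above 8x ULN

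*SAP*

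**What the plan says.** Protocol section 9.1.2 introduces its liver stopping rules with "Discontinue study drug administration permanently if any of the following occur" and gives four criteria for ALT or AST:

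- above 8x ULN, with no further condition;
- above 5x ULN for longer than two weeks;
- above 3x ULN together with bilirubin above 2x ULN or INR above 1.5;
- above 3x ULN together with listed symptoms or eosinophilia.

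SAP section 9.5.2 plans two relevant displays. The ALT/AST shift tables use three categories, the highest being above 3x ULN. The second display is described as follows: "a summary table is provided for the number and percentage of patients meeting the following threshold levels at any time during the study". That list opens with "5x ULN for more than 2 weeks", continues with the two above-3x combinations, and ends with BNP above 200 pg/mL, low magnesium and NT-proBNP above 1000 pg/mL. The three aminotransferase rows do not name the analyte.

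For fluid status, Protocol section 9.1.1 says that a patient whose BNP exceeds 100 pg/mL at a level "that represents a doubling (or more) of BNP levels from Day 1 should have an unscheduled telephone contact immediately". The SAP table has no row for that combination.

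**The concern.** Safety and tolerability is one of the two primary objectives (Protocol section 6.1.1), and aminotransferase elevation is among the first risks the protocol describes (section 5.1.2.2). The threshold table otherwise follows the protocol closely: three of the four liver criteria are carried over, and the magnesium row matches Protocol section 9.1.5. The SAP change summary records that threshold levels were added in version 2. Neither document gives a reason for leaving out the fourth criterion, so the omission looks like an oversight.

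The omitted criterion is the only one that depends on the enzyme level alone. It is also the one least likely to be picked up by the other rows, because stopping drug promptly shortens the time spent above 5x ULN. At stake is a simple by-arm count of patients who met a mandatory stopping rule of this trial.

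**Working it through.** The plan states no figure to reproduce here. The check is a line-by-line comparison, followed by hypothetical patients run through the six SAP rows.

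**1. ALT/AST criteria side by side**

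| Protocol 9.1.2, permanent discontinuation | Row in SAP 9.5.2 table |
|---|---|
| ALT or AST above 8x ULN | none |
| above 5x ULN for more than two weeks | yes |
| above 3x ULN with bilirubin above 2x ULN or INR above 1.5 | yes |
| above 3x ULN with symptoms or eosinophilia | yes |

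**2. Hypothetical ALT profiles** (normal bilirubin and INR, no symptoms, BNP, NT-proBNP and magnesium within the table's limits)

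- ALT 9x ULN, above 5x for 10 days: the protocol criterion is met because 9 > 8. SAP rows met: none, since 10 days is less than 14 and the two above-3x rows need a further condition.
- ALT 9x ULN, above 5x for 16 days: counted in the more-than-two-weeks row, since 16 > 14.

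A patient above 8x ULN can therefore miss every row, but need not. In the shift table both patients fall in the above-3x category, together with a patient at 3.1x.

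**3. How many patients this could concern**

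Protocol section 5.1.2.2 reports about 4% to 11% of patients above 3x ULN in earlier studies. With 35 active patients: 35 × 0.04 = 1.4 and 35 × 0.11 = 3.85, or about 3.9. Patients above 8x are a subset of these. The documents give no rate above 8x, so if the earlier rates apply here the expected number lies between 0 and about 3.9.

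**4. The BNP contact prompt (lesser point)**

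The prompt needs BNP above 100 and at least 2 × Day 1. The SAP row needs BNP above 200. A prompted patient is missed by the BNP row when the on-study value is at most 200:

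| Day 1 BNP (pg/mL) | On-study values that meet the prompt but not the BNP row |
|---|---|
| 50 | above 100, up to 200 |
| 60 | 120 to 200 |
| 75 | 150 to 200 |
| 90 | 180 to 200 |
| 100 | 200 only |
| above 100 | none (2 × Day 1 already exceeds 200) |

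A rise from 60 to 150 is not counted in the BNP row, and a rise from 60 to 201 is.

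The prompt cannot be recovered from SAP change-from-baseline values. SAP section 5.4.5 averages all pre-dose laboratory values, while the prompt uses Day 1. For example, with Screen A 90 and Day 1 60, the SAP baseline is (90 + 60)/2 = 75. An on-study value of 120 is 120/60 = 2.0 times Day 1 but 120/75 = 1.6 times the SAP baseline.

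**The case against.** A reader might infer that a patient above 8x ULN would go unreported. The documents do not support that.

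- The patient is counted in the above-3x shift category.
- SAP section 9.5.2.1 plans eDISH plots and states: "A listing of subjects with abnormal ALT, AST, or TBL will also be provided".
- Protocol section 11.6 treats a laboratory change that requires action as clinically significant, so a case that forces discontinuation would normally be recorded as an adverse event. It would then enter the table of treatment-emergent events leading to permanent discontinuation (SAP section 9.1.2). Reasons for stopping treatment are also tabulated (SAP section 6.1).
- By-visit laboratory summaries include the maximum (SAP sections 5.2 and 9.5.1), although an unscheduled peak can drop out of them because only the value closest to the target day is used (SAP section 5.5.3).

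With so few expected cases, a listing would identify each one. All of this stands, and it limits the point to a missing labelled count.

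A reader might also put the BNP omission on a level with the liver one. That does not hold either. The BNP prompt calls for a telephone contact, and stopping drug depends on suspected clinically important fluid retention. The SAP's 200 pg/mL is not arbitrary: Protocol section 9.1.1 uses it to define volume overload at baseline, and section 8.2 excludes patients with "B-type natriuretic peptide (BNP) level > 200 pg/mL at Screen A visit". NT-proBNP above 1000 pg/mL is counted in the same table, and weight gain of 2.3 kg or more is counted in SAP section 9.6.1. A patient missed by the BNP row may be counted in either.

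Finally, nothing obliges an SAP to turn every management trigger into a summary row. That is fair as a general rule. It has less force here, because the table already carries the other three criteria of the same list and its reader may take it as complete.

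**Conclusion.** The omission is real and small. The SAP table covers three of the four ALT/AST permanent-discontinuation criteria. A patient who stops drug for a brief, asymptomatic rise above 8x ULN can meet none of its rows, and the shift table does not separate that patient from one just above 3x ULN. The effect is on completeness of reporting by arm. It does not touch the efficacy analysis, and the underlying cases remain visible elsewhere.

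The number of patients affected is unknown. It is bounded by the roughly 1.4 to 3.9 active patients expected above 3x ULN, assuming that earlier rates carry over and 35 patients are treated with active drug, and it may be zero. The BNP gap exists only for Day 1 values up to 100 pg/mL and concerns a contact prompt, so it is secondary. The point is about reporting only and takes no position on whether any clinical threshold is right.

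**What to change.** In SAP section 9.5.2:

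1. Add a row for ALT or AST above 8x ULN at any time during the study, so that all four protocol criteria are counted by arm.
2. Name ALT or AST in the three existing aminotransferase rows.
3. Optionally, add a row for BNP above 100 pg/mL and at least twice the Day 1 value. Calculate the ratio from the Day 1 measurement and not from the averaged baseline of SAP section 5.4.5. A footnote should say that BNP above 200 pg/mL, NT-proBNP above 1000 pg/mL and weight gain of 2.3 kg or more are already counted.

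No further shift categories or enzyme cut-offs are needed to close the mismatch. The cost is one or two extra table rows programmed from laboratory data that the trial already collects. No new assessments are required, and no inference changes, since SAP section 9 plans no formal testing of safety.
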